## 11.4 End of Study Participation

Provision of study medication will not be continued beyond the study period. After the study ends, participants should follow up with their usual care physician to determine appropriate future treatment. Participants' GPs will be made aware of their involvement in the study from the point of consent. Participants will receive an "end of study" newsletter after the end of the study. If the study finishes early, participants will receive a final annual questionnaire in addition to the "end of study" newsletter.

## 11.5 Schedule of Assessments

Please see Appendix 1.

## 12 Assessment of Safety

Oxford DTU are hosting the trial management system which will collect the information to facilitate safety reporting to the Sponsor at the agreed interval described in sections 12.5 and 12.6.

# 12.1 Definitions

#### 12.1.1Adverse event (AE)

Any untoward medical occurrence in a patient or clinical trial participant administered a medicinal product and which does not necessarily have a causal relationship with this treatment.

An adverse event can therefore be any unfavourable and unintended sign (including an abnormal laboratory finding), symptom, or disease temporally associated with the use of an investigational medicinal product, whether or not considered related to the investigational medicinal product.

Adverse events will be recorded from the point of informed consent, regardless of whether the participant has received a medicinal product and evaluated at local study centres by a member of the study team with appropriate clinical expertise. This includes evaluation of its seriousness, expectedness and causality.

# 12.1.2Adverse Reaction to an IMP (AR)

All untoward and unintended responses to an investigational medicinal product

related to any dose administered. All adverse events judged by either the reporting investigator or the sponsor as having a reasonable causal relationship to a medicinal product qualify as adverse reactions. The expression reasonable causal relationship means to convey in general that there is evidence or argument to suggest a causal relationship.

## 12.1.3Unexpected adverse reaction

An adverse reaction, the nature, or severity of which is not consistent with the applicable reference safety information (RSI) (e.g. investigator's brochure for an unapproved investigational product or summary of product characteristics (SmPC) for an authorised product).

When the outcome of the adverse reaction is not consistent with the applicable RSI this adverse reaction should be considered as unexpected.

The term "severe" is often used to describe the intensity (severity) of a specific event. This is not the same as "serious," which is based on participant/event outcome or action criteria.

## 12.1.4 Serious adverse event (SAE) or serious adverse reaction (SAR)

Any untoward event or medical occurrence that at any dose:

- Results in death,
- Is life-threatening, (NOTE: The term "life-threatening" in the definition of "serious" refers to an event in which the participant was at risk of death at the time of the event; it does not refer to an event which hypothetically might have caused death if it were more severe)
- Requires inpatient hospitalisation or prolongation of existing hospitalisation,
- Results in persistent or significant disability/incapacity, or
- Is a congenital anomaly/birth defect.
- Other important medical events deemed significant by the investigator. **NOTE**: Other events that may not result in death, are not life threatening, or do not require hospitalisation, may be considered a serious adverse event when, based upon appropriate medical judgement, the event may jeopardise the participant and may require medical or surgical intervention to prevent one of the outcomes listed above

#### 12.1.5 Suspected Unexpected Serious Adverse Reaction (SUSAR)

A serious adverse reaction, the nature and severity of which is not consistent with the information set out in the Reference Safety Information.

#### 12.2 Reference Safety Information

For this study the Reference Safety Information is: Section 4.0 of the SmPC for Glucophage prolonged release metformin

(http://www.medicines.org.uk/EMC/medicine/20952/SPC)

# 12.2.1 Expected Adverse Reactions/Serious Adverse Reactions (AR /SARs)

The common side effects of metformin include GI upset and diarrhoea. Hypoglycaemia does occur rarely and lactic acidosis is a very rare but serious adverse effect.

Evidence from participants with NDH in the DPP suggests that hypoglycaemia is not expected and serious adverse effects will be very rare [18]. GLINT participants will be

advised about the symptoms suggestive of hypoglycaemia (such as tachycardia, palpitations, shakiness, sweating, inability to concentrate, dizziness, hunger, blurred vision, obvious impairment of motor function, confusion or inappropriate behaviour which reverse after intake of carbohydrates) and how to respond. Serious hypoglycaemia (requiring the assistance of another person) will be regarded as a serious adverse event triggering the safety reporting mechanism described in section 11.5 below. Each participant will be issued with a card indicating that he/she is participating in a research study. This card will indicate the name and the phone number of the investigational site to be contacted in case of an emergency, including any episode of suspected hypoglycaemia requiring the assistance of another person. The card will also specify temporary interruption of treatment with study medication if participants undergo general anaesthesia or investigation with iodine-containing X-ray contrast media, and if participants are at risk of tissue hypoxia or sudden deterioration in renal function, for example due to severe dehydration or infection, shock, sepsis, acute heart or respiratory failure, hepatic impairment and recent myocardial infarction.

An extremely rare but potentially serious side-effect of metformin is lactic acidosis. The risk of lactic acidosis is increased among people with chronic kidney disease (CKD stage 3b or worse). Consequently, we will exclude individuals with eGFR<45ml/min and measure creatinine at baseline, three and six months in the feasibility phase. Participants' GPs will be reminded of contraindications to metformin and this rare side effect and the need to discontinue study medication in these eventualities (i) when they are informed that their participant has entered the study; (ii) at the four month questionnaire phase in the feasibility phase; and (iii) annually thereafter when receiving their questionnaire. Written reminders detailing the action to be taken by participants in the event of a severe illness, including renal failure, will be sent to participants at four month questionnaire phase in the feasibility phase and every twelve months when they receive their annual questionnaire. Any participant who develops chronic kidney disease (CKD stage 3b or worse, eGFR<45ml/min) during the study will not be offered further metformin/placebo. The mechanism for reporting and responding to potential adverse events is shown in the safety reporting section 12.4 and 12.5 below.

Chronic metformin use has been associated with Vitamin B12 deficiency [24]. Severe B12 deficiency can result in neuropathic symptoms that can be mistaken for diabetic neuropathy. However, the strength of this association has varied in epidemiologic studies and the clinical significance of mild B12 deficiency syndromes is unclear. The GLINT feasibility phase will measure B12 levels at baseline and 6 month visits. If a participant has a B12 level < 200 pg/ml the results will be reviewed by a study clinician and their GP contacted if necessary. The results will be reviewed following the feasibility phase to inform a decision whether it is necessary to continue monitoring B12 levels in the full study.

#### 12.3 Expected Adverse Events/Serious Adverse Events (AE/SAE)

Expected events, which may or may not fulfil the criteria for serious are listed in Appendix 2 (Modified safety reporting). Any events, that occur, that meet serious criteria, which are not listed in Appendix 2, will also be collected and reported.

#### 12.4 Recording and evaluation of adverse events

#### Non-serious Adverse Events

AEs will only be recorded if they result in cessation of the drug and the event is considered related to the drug.

The following information will be recorded: description of event, date of onset, dosage and any required changes, assessment of seriousness, assessment of expectedness, relevant medical history, concomitant medications, causality assessment and resolution/outcome.

**Serious Adverse Events** All events that fulfil the criteria for serious will be collected and reported, however those detailed in Appendix 2 will be subject to a modified safety reporting plan. These events include (1) Primary and secondary study endpoints, (2) Other cardiovascular events of interest (that may be associated with the primary CV endpoints and are included among items that will be sent for review by the CEC), (3) other non-cardiovascular events of interest (e.g. incident cancer, incident T2DM), (4) known common toxicities of metformin.

Any SAE which is not listed in appendix 2 will be recorded using the AE/SAE eCRF.

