Funding for the feasibility phase, which will be carried out in two UK regions, is provided by the NIHR Health Technology Assessment programme. If successful, this will lead into the full study and recruitment will be expanded to a further six geographical regions in the UK.

The study duration is driven by the time to accumulate 1,046 confirmed events in the primary composite endpoint. Initially, 250 participants will be enrolled in the study. The enrolment of a further 12,648 individuals will depend on the outcome of assessment of data from the initial feasibility phase including demonstration of the feasibility of general practice and participant recruitment, the feasibility of randomisation and distribution of study medication, the acceptability of adverse event reporting and outcome assessment and the safety of metformin and the proposed frequency of monitoring of

renal function and B12 levels. Demonstration of a treatment effect within the limited duration of follow-up in the feasibility phase is not an objective.

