# 9.6.1 Discontinuation of study medication

Discontinuations from study treatment may occur for protocol-specified reasons (see below), due to the judgment of the primary investigator, or due to the participant's decision.

Protocol specified reasons for study drug discontinuation are:

• An adverse event which requires discontinuation of the study medication or results in inability to continue to comply with study procedures. Study drug can be resumed if the event resolves.

• Participant refuses follow up via participant annual questionnaire

• Development of chronic kidney disease (CKD stage 3b or worse, eGFR<45ml/min).

•Participant is temporarily not contactable

Participants are considered temporarily not contactable in the following situations:

- •Telephone contacts are made at 4 and 8 weeks. Sites will make three attempts to call the participant during this period. After three failed call attempts the participant is lost to follow up and the drug supply is stopped.
- •The participants are asked to complete and send a questionnaire at 4 months, then annually. Failure to return the questionnaire will result in a repeat issue of the questionnaire at 4 weeks after the due date and also at 8 weeks if required. Continued failure to return the questionnaire within another month results in an attempt to call the participant. After three failed call attempts the patient is lost to follow up and the drug supply is stopped.

For participants who fulfil the above criteria, attempts will be made annually to reestablish contact. If contact is re-established and the participant agrees, the drug will be re-started.

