#### Note:

Participants who develop T2DM during the course of the study should be advised to continue taking study medication and their GP will be advised to consider adding either metformin, such that the daily dose does not exceed the permitted maximum, assuming the study medication is the active therapy (see Table 1), or an alternative glucose lowering drug if required.

GLINT study medication daily dose	Maximum additional daily amount of standard release metformin permitted	Maximum additional daily amount of prolonged release metformin permitted
500 mg (1 tablet)	2000 mg	1500 mg
1000 mg (2 tablets)	1500 mg	1000 mg
1500 mg (3 tablets)	1000 mg	500 mg

Table 1: Prescription of additional metformin for those developing T2DM during the study

Participants who become pregnant during the course of the study can continue taking study medication (28).

Participants who experience a possible CVD event during the study will be encouraged to continue taking study medication as long as there are no contraindications.

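### Section 12.4 keeps non-serious B12 deficiency out of the adverse event record when it is treated and study drug continues, although section 12.2.1 associates it with chronic metformin use

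*Protocol*

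**What the plan says.** Section 12.4 of the protocol sets the recording rule for non-serious events: "AEs will only be recorded if they result in cessation of the drug and the event is considered related to the drug". Serious events are all collected (sections 12.3 and 12.4), with a modified reporting route for those listed in Appendix 2.

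Section 12.2.1 states: "Chronic metformin use has been associated with Vitamin B12 deficiency". It adds that severe deficiency "can result in neuropathic symptoms that can be mistaken for diabetic neuropathy", that the strength of the association has varied between studies, and that the importance of mild deficiency is unclear. B12 is measured at baseline and 6 months in the feasibility phase. For a value below 200 pg/ml, "the results will be reviewed by a study clinician and their GP contacted if necessary". The feasibility results are then used "to inform a decision whether it is necessary to continue monitoring B12 levels in the full study". Section 7 likewise lists, among the matters the feasibility phase should settle, "the safety of metformin and the proposed frequency of monitoring of" renal function and B12. A note to the flow chart in section 6 says that baseline B12 is not planned for the full study, subject to the feasibility safety results.

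The list in section 9.6.1 that opens "Protocol specified reasons for study drug discontinuation are" does not name B12 deficiency. Appendix 2 gives only gastrointestinal upset or diarrhoea and hypoglycaemia as known reactions to metformin. Section 10.4 says that follow-up in the full study is postal after the baseline visit.

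**The concern.** The protocol names a harm of long-term metformin and then applies a recording rule that the usual management of that harm does not satisfy. B12 deficiency is ordinarily corrected by replacement, not by stopping metformin, and section 12.2.1 prescribes nothing different. The diagnosed cases most likely to arise in a trial lasting five to seven years are therefore the ones that section 12.4 leaves out.

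At stake is a randomised, placebo-controlled comparison of diagnosed deficiency in people without diabetes. Section 12.2.1 itself describes the evidence as uncertain, which is a reason to keep the cases that come to notice. An analysis plan written later cannot restore event records, with onset, causality and outcome, that the protocol says are not to be made.

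**Working it through.** The plan states no figure on this point. The check sets the rule beside the pathway that a typical case would follow.

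1. **Which rule governs.** Section 12.1.1 says in general terms that adverse events are recorded from consent. Section 12.4 is the specific rule and is exclusive, and section 12.2.1 refers the reader to sections 12.4 and 12.5 for the mechanism. Section 12.4 therefore governs.

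2. **Relatedness condition.** Under section 12.4.2, a causality rating of possible already counts as drug-related. Diagnosed B12 deficiency in someone who may be taking metformin could readily meet that bar, so relatedness is not the main filter.

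3. **Cessation condition.** Section 12.2.1 answers a low B12 with review and GP contact. Section 9.6.1 does not name deficiency as a stopping reason. Its general item, an adverse event that requires discontinuation, applies only if a clinician decides that the drug must stop. Participants with new diabetes are also steered towards continuing: "Participants who develop T2DM during the course of the study should be advised to continue taking study medication". For a deficiency treated by the GP with study drug continued, the condition is not met.

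4. **Result.** Recording requires cessation and relatedness together. Cessation is false, so the event is not recorded, whatever the answer on relatedness.

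5. **Other routes.**
   - Serious cases: collected (sections 12.3 and 12.4), so the gap is confined to non-serious cases.
   - Feasibility phase: B12 values at 0 and 6 months are presented by arm (section 15.2), so the gap matters mainly in the full study.
   - Full study: annual participant and GP questionnaires ask about adverse events, and the GP form asks for current prescriptions (section 11.3.1). Section 12.4.3 allows events to be noted by questionnaire. Traces may exist, but section 12.4 does not turn them into adverse event records.

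6. **Scale.** The protocol gives no rate of diagnosed deficiency, so the number of cases lost cannot be calculated. As a unit conversion only, the metformin arm is 12,898 / 2 = 6,449 people. Each percentage point of diagnosed deficiency would be 6,449 × 0.01 ≈ 64 people, or 64.49 × 0.84 ≈ 54 with the 16% loss to follow-up assumed in section 15.3. Only the non-serious cases among them who stay on study drug would go unrecorded.

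**The case against.** The strongest reply is that selective recording of non-serious events is a deliberate and legitimate choice in a pragmatic trial of a long-used drug, and that section 12.4 does not contradict section 12.2.1, which treats B12 as a laboratory monitoring question. Much of the information may also survive in the annual questionnaires and GP medication lists, which the trials unit enters as data (section 16.3). Disabling neuropathy, or any case judged medically important, is serious under section 12.1.4 and is collected. What remains is milder disease of uncertain importance. All of this stands and limits the weight of the point. It does not justify leaving a named harm under a rule that its usual management cannot satisfy.

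Four stronger readings are tempting and are not supported.

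- A reader might infer that the full study will have no B12 surveillance. Sections 7, 11.3.2 and 12.2.1 leave that decision open, and the flow-chart note concerns the baseline measurement only.
- A reader might infer that the randomised comparison is lost altogether. The questionnaires and prescriptions may support part of it; how much depends on forms that are not shown.
- A reader might size the loss from the feasibility sampling: about 250 / 2 = 125 metformin participants seen for six months, against five to seven years of treatment. That describes how little the feasibility measurements can say about long-term deficiency. It does not measure how many diagnosed cases section 12.4 leaves out.
- A reader might argue that all neuropathy should be exempted because of the misattribution that section 12.2.1 mentions. Neuropathy attributed to diabetes may fail on relatedness as well as cessation. It is also non-specific, and its frequency can differ between arms through diabetes incidence, itself a secondary endpoint.

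**Conclusion.** The concern holds in a limited form. As written, section 12.4 keeps non-serious, diagnosed B12 deficiency out of the adverse event record whenever study drug continues, which is the likely course under the protocol's own pathway. The effect falls mainly on the full study. Its size is unknown, and nothing in the document allows it to be estimated.

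The conclusion assumes that diagnosed deficiency is usually treated without stopping study drug. The protocol does not say so outright, but sections 12.2.1 and 9.6.1 point that way. It also assumes that section 12.4 is followed literally in preference to the general statement in section 12.1.1. This is an inexpensive improvement in safety ascertainment. It does not threaten the primary analysis or the detection of serious harm.

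**What to change.** In section 12.4, name physician-diagnosed B12 deficiency, including neuropathy or anaemia that the treating clinician attributes to it, as an event of interest. Record it when the participant or GP reports it, whether or not study drug is stopped and whether or not it is judged related. Do not exempt neuropathy in general. Tabulate these events by randomised arm, alongside new B12-replacement prescriptions taken from the existing GP medication item. The tabulation can be specified in the statistical analysis plan, but the recording has to be fixed in the protocol.

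The cost is one clause and a modest amount of extra event entry: each record needs the items listed in section 12.4 and clinical evaluation at the local centre. No visit or blood sample is added. Three limits should be stated with the results. Routine diagnosis misses subclinical deficiency. Without a baseline B12, some cases may be pre-existing, although randomisation should balance these between arms. Open-label metformin after a diabetes diagnosis (sections 9.6.1 and 10.7) may dilute the contrast.

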## 12.4.1 Assessment of seriousness

Seriousness is assessed against the criteria in section 12.1.4. This defines whether the event is an adverse event, serious adverse event or a serious adverse reaction

#### 12.4.2 Assessment of causality

- Definitely: A causal relationship is clinically/biologically certain. This is therefore an Adverse Reaction
- Probable: A causal relationship is clinically / biologically highly plausible and there is a plausible time sequence between onset of the AE and administration of the investigational medicinal product and there is a reasonable response on withdrawal. **This is therefore an Adverse Reaction**.
- Possible: A causal relationship is clinically / biologically plausible and there is a plausible time sequence between onset of the AE and administration of the investigational medicinal product. **This is therefore an Adverse Reaction**.
- Unlikely: A causal relation is improbable and another documented cause of the AE is most plausible. This is therefore an Adverse Event.
- Unrelated: A causal relationship can be definitely excluded and another documented cause of the AE is most plausible. **This is therefore an Adverse Event**.

Unlikely and Unrelated causalities are considered NOT to be study drug related Definitely, Probable and Possible causalities are considered to be study drug related

A pre-existing condition must not be recorded as an AE or reported as an SAE unless the condition worsens during the study and meets the criteria for reporting or recording in the appropriate section of the CRF.

#### 12.4.3Recording of adverse events

Adverse events and adverse reactions may be recorded either in the participants medical notes, directly into the eCRF (which is considered source data) or via a questionnaire.

#### 12.5 Reporting serious adverse events

All serious adverse events are recorded in the eCRF through one of three paths:

•Direct participant contact with their study centre

Participants will be instructed to contact their study centre if they have any serious illness, a hypoglycaemic event that required the assistance of another person, are admitted to hospital for any reason, or discontinue their drug. Study centre staff will conduct a telephone interview to establish the participant's status and record any relevant clinical and safety data. If the centre staff have any concerns about the participant's status they will instruct the participant to contact their GP.

•Questionnaires (Month 4 & Annually thereafter)

The participant will receive an annual questionnaire that includes questions to capture safety and all relevant clinical data. This is returned by post to the DTU. Participants' GPs will also complete a similar questionnaire, which will also be mailed to the DTU, along with any relevant supporting documentation. Should any further data be required in addition to the questionnaires, the study staff will contact the participant and/or the participant's GP.

